
### Assessment of Intensity

The investigator will make an assessment of intensity for each AE and SAE reported during the trial and assign it to 1 of the following categories:

- Mild: An event that is easily tolerated by the subject, causing minimal discomfort and not interfering with everyday activities.
- Moderate: An event that causes sufficient discomfort and interferes with normal everyday activities.
- Severe: An event that prevents normal everyday activities. An AE that is assessed as severe should not be confused with a SAE. Severe is a category utilized for rating the intensity of an event; and both AEs and SAEs can be assessed as severe.

An event is defined as ‘serious’ when it meets at least 1 of the predefined outcomes as described in the definition of an SAE, NOT when it is rated as severe.

### Assessment of Causality

- The investigator is obligated to assess the relationship between trial treatment and each occurrence of each AE/SAE.
- The investigator will assess the relationship as either of the following:
  - **Related:** An AE will be considered “related” to the use of the IMP if there is evidence to suggest a reasonable possibility of a causal relationship between the IMP and the AE.
  - **Not Related:** An AE will be considered “not related” to the use of the IMP if there is no plausible causal relationship between the IMP and the AE.
- The investigator will use clinical judgment to determine the relationship.
- Alternative causes, such as underlying disease(s), concomitant therapy, and other risk factors, as well as the temporal relationship of the event to trial treatment administration will be considered and investigated.
- The investigator will also consult the Investigator’s Brochure and/or Product Information, for marketed products, in his/her assessment.
- For each AE/SAE, the investigator **must** document in the medical notes that he/she has reviewed the AE/SAE and has provided an assessment of causality.
- There may be situations in which an SAE has occurred and the investigator has minimal information to include in the initial report to the sponsor or designee. However, **it is very important that the investigator always make an assessment of causality for every event before the initial transmission of the SAE data to the sponsor or designee.**
- The investigator may change his/her opinion of causality in light of follow-up information and send a SAE follow-up report with the updated causality assessment.
- The causality assessment is one of the criteria used when determining regulatory reporting requirements.

**Table 13 Follow-Up of AEs and SAEs**

Follow-Up of AEs and SAEs

 
The investigator is obligated to perform or arrange for the conduct of supplemental measurements and/or evaluations as medically indicated or as requested by the sponsor or designee to elucidate the nature and/or causality of the AE or SAE as fully as possible. This may include additional laboratory tests or investigations, histopathological examinations, or consultation with other health care professionals.
 
If a subject dies during participation in the trial or during a recognized follow-up period, the investigator will provide the sponsor or designee with a copy of any post-mortem findings including histopathology.
 
New or updated information will be recorded in the originally completed eCRF.
 
The investigator will submit any updated SAE data to the sponsor or designee within 24 hours of receipt of the information.
 

**10.3.4 Reporting of SAEs and AESIs**
**Table 14 SAE/AESI Reporting to the Sponsor or Designee via an Electronic Data Collection Tool**

SAE/AESI Reporting to the Sponsor or Designee via an Electronic Data Collection Tool

 
The primary mechanism for reporting an SAE or AESI to the sponsor or designee will be the electronic data collection tool.
 
The site will enter the SAE/AESI data as soon as it becomes available within 24 hours of awareness.
 
If the electronic data collection tool is unavailable, then the site will use the paper SAE or AESI form (see next section).
 
After the trial is completed, the electronic data collection tool will be set to read-only to prevent the entry of new data or changes to existing data.
 
If a site receives a report of a new SAE or AESI from a trial subject or receives updated data on a previously reported SAE or AESI after the electronic data collection tool has been taken off-line, then the site can report this information on the paper SAE or AESI form (see next section) or to the sponsor or designee by telephone.
 

 

**Table 15 SAE/AESI Reporting to the Sponsor or Designee via Paper Form (if needed)**

SAE Reporting to the Sponsor or Designee via Paper Form

• If the electronic data collection tool is unavailable, then the site will use the paper SAE/AESI form. The SAE or AESI paper form should be used to electronically transmit this information to the sponsor or designee.

• Contacts for electronic transmission of the paper SAE/AESI form are provided in the Operations Manual.

• In rare circumstances and in the absence of facsimile equipment, notification by telephone is acceptable with a copy of the SAE or AESI data collection tool sent by overnight mail or courier service.

• Initial notification via telephone does not replace the need for the investigator to complete and sign the appropriate SAE or AESI form within the designated reporting time frames.

• 

## **10.4 Appendix 4: Contraceptive Guidance and Collection of Pregnancy Information**

### **10.4.1 Definitions**

#### **10.4.1.1 Highly Effective Form of Contraception**

A highly effective form of contraception is defined as follows:

- Combined (estrogen and progestogen containing) hormonal contraception associated with inhibition of ovulation:
  - Oral
  - Intravaginal
  - Transdermal
- Progestogen-only hormonal contraception associated with inhibition of ovulation:
  - Oral
  - Injectable
  - Implantable
- Intrauterine device
- Intrauterine hormone-releasing system
- Bilateral tubal occlusion

- Vasectomized partner

#### **10.4.1.2      *Contraception and Pregnancy Avoidance Procedures***

The following definitions apply for contraception and pregnancy avoidance procedures:

A woman is considered a WOCBP following menarche and until becoming postmenopausal unless permanently sterile. Permanent sterilization methods include hysterectomy and bilateral oophorectomy.

A postmenopausal state is defined as no menses for 12 months without an alternative medical cause.

Sterilized male subjects should be at least 1 year postbilateral vasectomy and have confirmed that they have obtained documentation of the absence of sperm in the ejaculate or have had bilateral orchidectomy.

#### **Collection of Pregnancy Information**

##### **Male subjects with partners who become pregnant**

- The investigator will attempt to collect pregnancy information on any male subject's female partner who becomes pregnant while the male subject is in this trial. This applies only to male subjects who receive IMP.
- After obtaining the necessary signed informed consent from the pregnant female partner directly, the investigator will record pregnancy information on the appropriate form and submit it to the sponsor within 24 hours of learning of the partner's pregnancy. The female partner will also be followed to determine the outcome of the pregnancy. Information on the status of the mother and child will be forwarded to the sponsor. Generally, the follow-up will be no longer than 6 to 8 weeks following the estimated delivery date. Any termination of the pregnancy will be reported regardless of fetal status (presence or absence of anomalies) or indication for the procedure.

##### **Female subjects who become pregnant**

- The investigator will collect pregnancy information on any female subject who becomes pregnant while participating in this trial. Information will be recorded on the appropriate form and submitted to the sponsor within 24 hours of learning of a subject's pregnancy.
- The subject will be followed to determine the outcome of the pregnancy. The investigator will collect follow-up information on the subject and the neonate and the information will be forwarded to the sponsor. Generally, follow-up will not be required for longer than 6 to 8 weeks beyond the estimated

delivery date. Any termination of pregnancy will be reported, regardless of fetal status (presence or absence of anomalies) or indication for the procedure.

- While pregnancy itself is not considered to be an AE or SAE, any pregnancy complication or elective termination of a pregnancy will be reported as an AE or SAE. A spontaneous abortion is always considered to be an SAE and will be reported as such. Any post-trial pregnancy related SAE considered reasonably related to the trial treatment by the investigator will be reported to the sponsor as described in [Section 8.4.4](#). While the investigator is not obligated to actively seek this information in former trial subjects, he or she may learn of an SAE through spontaneous reporting.
- Any female subject who becomes pregnant while participating in the trial will discontinue trial treatment and be withdrawn from the trial.

## 10.5 Appendix 5: Inducers and Inhibitors of Cytochrome P450 3A

CYP 3A Inhibitors	CYP 3A Inducers
HIV antivirals	HIV antivirals
Indinavir	Efavirenz
Nelfinavir	Nevirapine
Ritonavir	Etravirine
Saquinavir	Miscellaneous
Boceprevir	Barbiturates
Lopinavir/ritonavir	Carbamazepine
Amprenavir	Eslicarbazepine
Atazanavir	Glucocorticoids (systemic)
Telaprevir	Modafinil
Darunavir/ritonavir	Oxcarbazepine d
Fosamprenavir	Phenobarbital
Antibiotics	Phenytoin
Clarithromycin	Pioglitazone
Erythromycin	Rifabutin
Telithromycin	Rifampin
Ciprofloxacin	St. John's wort
Anti-infectives	Troglitazone
Itraconazole	Bosentan
Ketoconazole	Nafcillin
Fluconazole	Avasimibe
Posaconazole	
Voriconazole	
Anti-anginal therapy	
Diltiazem	
Verapamil	
Anti-cancer therapy	
Crizotinib	
Imatinib	
Miscellaneous	
Nefazodone	
Aprepitant	
Grapefruit juice a,b	
Conivaptan	
Mibepradil c	

a The effect of grapefruit juice varies widely among brands and is concentration-, dose-, and preparation dependent. Studies have shown that it can be classified as a “strong CYP3A inhibitor” when a certain preparation was used (eg, high dose, double strength) or as a “moderate CYP3A inhibitor” when another preparation was used (eg, low dose, single strength).

b A 2-week washout prior to dosing is required if grapefruit juice was being consumed continually.

c Withdrawn from the United States market.

d Doses >900 mg/day.

## 10.6 Appendix 6: Abbreviations

Abbreviation	Definition
AE	Adverse event
AED	Anti-epileptic drug
AESI	Adverse event of special interest
ALT	Alanine aminotransferase
APMP	Abuse Potential Monitoring Plan
AST	Aspartate aminotransferase
BID	Twice daily
BZD	Benzodiazepine
CBC	Complete blood count
CGI-S	Clinical Global Impression-Severity
CSR	Clinical study report
C-SSRS	Columbia-Suicide Severity Rating Scale
ECG	Electrocardiogram
eCRF	Electronic case report form
eDiary	Electronic diary
ESAM	Events Subject to Additional Monitoring
EudraCT	European Clinical Trials Database
GABA A	γ-aminobutyric acid type A
GCP	Good Clinical Practice
ICF	Informed Consent Form
ICH	International Council for Harmonisation
IEC	Independent Ethics Committee
IMP	Investigational medicinal product
IRB	Institutional Review Board
mCIWA-B	Modified Clinical Institute Withdrawal Assessment–Benzodiazepines
MedDRA	Medical Dictionary for Regulatory Activities
MHI	Medication handling irregularity
MHP	Mental Health Professional
PAM	Positive allosteric modulator

**Abbreviation      Definition**

PGI-C	Patient Global Impression of Change
PK	Pharmacokinetic
SAE	Serious adverse events
SAP	Statistical analysis plan
TEAE	Treatment-emergent adverse event
TESC	The Epilepsy Study Consortium
ULN	Upper limit of normal range
US	United States
WBC	White blood cell
WOCBP	Women of childbearing potential

**10.7 Appendix 7: Protocol Amendment History**

Document History	
Document:	Date (Day-Month-Year)
Version 3.0	14 Jul 2020
Version 2.0	26 Nov 2019
Original Protocol Version 1.0	30 Oct 2019

The Protocol Amendment Summary of Changes Table for the current amendment is located directly before the Table of Contents.

**Amendment: Protocol Version 2.0 (26 Nov 2019)**

This amendment is considered to be substantial based on the criteria set forth in Article 10(a) of Directive 2001/20/EC of the European Parliament and the Council of the European Union.

**Overall Rationale for the Amendment:** To revise relevant sections of the protocol to minimize potential risk to subjects.

Section # and Name	Description of Change	Brief Rationale
1.2 Schema 1.3 Schedule of Activities	
Changed Contact Only visits during Maintenance Phase to in-clinic visits
 
Scheduled additional safety laboratory blood samples during Maintenance Phase (ie, for visits that been Contact Only in original protocol) and at Post-Treatment Follow-up in-clinic visit
 
Reduced intervals between some Maintenance Phase visits such that interval between visits was not more than 4 weeks
	Monitoring of new potential risk of bone marrow suppression and decrease in peripheral hematologic parameters
2.3 Benefit/Risk Assessment 5.2 Exclusion Criteria 7.3 Individual Subject Discontinuation 8.4.6.2 Hematologic Abnormalities	
Added potential risk of bone marrow suppression and decrease in peripheral hematologic parameters
 
Updated relevant risk minimization measures, exclusion criterion, criteria for discontinuation of IMP, and added new AESI subsection
	Update relevant protocol section with new potential risk of bone marrow suppression and decrease in peripheral hematologic parameters
8.3.2 Vital Sign Measurements	Reworded paragraph about blood pressure measurement	Simplification of vital signs collection procedure
Table 9 Protocol-Required Safety Laboratory Assessments	Added chloride and bicarbonate	Additional biochemistry labs for safety monitoring
10.4 Appendix 4: Contraceptive Guidance and Collection of Pregnancy Information	Revision of definitions and language for pregnancy avoidance procedure	Consistency with preceding double-blind protocol
Overall	Minor grammatical and wording corrections/clarifications made throughout protocol	
Reflect changes to visit numbers, visit timing, and visit types (ie, contact visits changed to in-clinic visits), due to changes to schedule of activities
 
Correct errors in original protocol

Abbreviations: AESI = adverse event of special interest; IMP = investigational medicinal product; WBC = white blood cell.

1. INTRODUCTION

This document describes the statistical methods and data presentations to be used in the summary and analysis of data from Protocol CVL-865-SZ-002. Background information is provided for the overall study design and objectives. The reader is referred to the study protocol and case report forms (CRFs) for details of study conduct and data collection.

1.1. Study Overview

[figure not shown]
This is a 57-week, active-treatment, open-label extension trial designed to assess the long-term safety and tolerability of CVL-865 as adjunctive therapy in subjects with focal onset seizures. Enrollment into the trial will consist of eligible subjects who completed the Maintenance Phase of Trial CVL-865-SZ-001.

Eligible subjects will enter this trial directly after completing Visit 4 (end of Maintenance Phase) of Trial CVL-865-SZ-001. The efficacy and safety assessments from Visit 4 of Trial CVL-865-SZ-001 will serve as the baseline assessments for the open-label trial for any assessments that are not unique to the open-label trial. All subjects must provide informed consent to participate in the open-label trial before any baseline assessments that are unique to the open-label trial are performed.

1.1.1. Study Design

This trial is designed with a maximum duration of approximately 61 weeks during which the subjects will receive CVL-865. The trial consists of the following:

- Up to 57-week Treatment Period consisting of the following:
 - 2-week double-blind Titration Phase
 - 52-week Maintenance Phase
 - 3-week Taper Phase
- 4-week Follow-up Period

Figure 1: Trial Schematic

Abbreviations: AED = anti-epileptic drug; BID = twice daily; OLE = open-label extension; Wk = week.

1.2. Sample Size Considerations

The sample size is not based on statistical power considerations. The trial population will be derived from eligible subjects from the double-blind, proof-of-concept Trial CVL-865-SZ-001. Approximately 120 subjects are expected to complete Trial CVL-865-SZ-001 and be eligible for enrollment in Trial CVL-865-SZ-002.

1.3. Measures to Minimize Bias: Randomization and Blinding

1.3.1. Subject Assignment to Treatment

All patients will receive CVL-865.

1.3.2. Blinding

This is an open-label trial with all subjects assigned to treatment with CVL-865. To ensure that the treatment assignments in the Phase 2 double-blind trial CVL-865-SZ-001 remain blinded for the subjects who rollover into the open-label trial, all subjects will be dispensed blinded CVL-865 tablets during the Titration Phase of this trial.

1.4. Treatment Period

Titration Phase:

Following enrollment in Trial CVL-865-SZ-002, subjects will enter a 2-week double-blind Titration Phase. Based on the blinded treatment group subjects were assigned to in Trial CVL-865-SZ-001, the dose will be increased in weekly intervals during the double-blind Titration Phase to a final dose of 25 mg BID as shown in table (Table 1). Subjects who completed the Maintenance Phase of Trial CVL-865-SZ-001 on a dose of 25 mg BID will remain on this dose (blinded) for the Titration Phase of Trial CVL-865-SZ-002.

Subjects who terminate during the double-blind Titration Phase (before Day 15) should receive 3 weeks of IMP to complete the Taper Phase.

Maintenance Phase:

Subjects will continue to receive treatment with CVL-865 25 mg BID throughout a 52-week Maintenance Phase. However, this daily dose of CVL-865 can be reduced to 17.5 mg BID to address tolerability issues upon investigator discretion. Following the Maintenance Phase, subjects will be tapered off investigational medicinal product (IMP) over 3 weeks in weekly intervals. A summary of the dosing schedule is provided in table below ([Table 1](#)).

A summary of the dosing schedule is provided below ([Table 1](#)).

Table 1. Summary of the Dosing Schedule

	Blinded Titration Phase		Maintenance Phase	Taper Phase		
Dose in Trial CVL-865-SZ-001	Day 1	Day 8	Day 15-Day 379	Day 386	Day 393	Day 400
Duration	2 weeks		52 weeks	3 weeks		
Placebo	5 mg BID	12.5 mg BID	25 mg BID	17.5 mg BID	10 mg BID	5 mg BID
CVL-865 7.5 mg BID	12.5 mg BID	17.5 mg BID	25 mg BID	17.5 mg BID	10 mg BID	5 mg BID
CVL-865 25 mg BID	25 mg BID	25 mg BID	25 mg BID	17.5 mg BID	10 mg BID	5 mg BID
Not applicable			17.5 mg BID ^a	10 mg BID	5 mg BID	2.5 mg BID

Abbreviations: BID = twice daily.

^a Subjects who had their dose reduced to 17.5 mg BID due to tolerability reasons during the Maintenance Phase

Follow-up Phase:

Follow-up telephone contact will be performed 7 ± 3 days after the last dose of IMP. A Safety Follow-up Visit will be made approximately 4 weeks after last dose of IMP.

2. OBJECTIVES AND ENDPOINTS

The trial objectives and endpoints are summarized in [Table 2](#).

Table 2. Objectives and Endpoints

Objectives	Endpoints
Primary: To assess the long-term safety and tolerability of CVL-865 as adjunctive therapy in subjects with focal onset seizures	
• Nature, frequency, and temporality of treatment-emergent adverse events (AE) (nonserious and serious), including abuse-related AEs and AEs related to medication handling irregularities• Clinically significant changes in electrocardiogram (ECG), vital sign measurements, clinical laboratory assessments, and physical and neurological examination results• Suicidality assessed using the Columbia- Suicide Severity Rating Scale (C-SSRS)• Withdrawal symptoms assessed using the Modified Clinical Institute Withdrawal Assessment – Benzodiazepines (mCIWA-B)
Exploratory: To assess the long-term efficacy of CVL-865 as adjunctive therapy in subjects with focal onset seizures	
• Focal onset seizure frequency per week over the Maintenance Phase• Seizure freedom• Seizure rate over time• Patient Global Impression of Change (PGI-C) score at each trial visit• Change from Baseline in Clinical Global Impression – Severity (CGI-S) score at each trial visit
Exploratory: To evaluate the plasma exposure of CVL-865	
• Summary listing of CVL-865 concentrations by dose and visit

3. KEY ASSESSMENTS AND DERIVATIONS

3.1. Efficacy Assessments

3.1.1. Seizure Frequency, Type and Seizure Rate

Subjects will record details regarding their seizures (frequency and type) in an eDiary. Any benzodiazepine (BZD) use will also be recorded in the diary.

Seizure rate is defined as the total number of focal onset seizures over the analysis period of interest divided by the total number of days with no missing seizure counts in the corresponding period. Seizure frequency will be defined as the seizure rate multiplied by the days within the period of interest. For cluster seizures, which are a group of seizures too numerous to count, the number of cluster episodes will be included as one seizure event. Unless otherwise specified, Seizure rate will only be calculated for focal onset seizures, which include focal aware seizures without motor signs, focal aware seizures with motor signs, focal impaired awareness seizures and focal to bilateral tonic-clonic seizures.

3.1.2. Seizure Freedom

Seizure freedom will be represented as a binary outcome defined as having no seizures during the maintenance period.

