4.2. Analysis Periods

The start and end dates of each analysis period (following the study design) are used for the classification of efficacy data. The exact start and end of each of these periods is described for calculation purposes in [Table 3](#). Seizure frequency for each analysis period will be calculated based on [Table 3](#).

Table 3. Definition of Analysis Periods for Efficacy Data

Analysis Period	Duration	Start Date	End Date
Extension Titration Phase	~2 Weeks	Study Day, 1	The lesser of: Day 15 (Visit 2) minus 1 or **Early termination (minus 1) or End of Treatment
Extension Maintenance Phase	~52 Weeks	Day 15 (Visit 2)	The lesser of: ***Day 379 (Visit 15) minus 1 or **Early termination (minus 1) or End of Treatment
Extension Taper Phase	~3 Weeks	Day 379 (Visit 15) or **Early termination	End of Treatment

** If a subject experiences early termination from the study and continues to Taper Phase, end dates will be bound by early termination minus 1, while the start of Taper Phase will begin on the date of early termination.

*** If a subject continues to Taper Phase from Maintenance Phase

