5. STATISTICAL ANALYSIS METHODS

5.1. General Considerations

Descriptive statistical methods will be used to summarize the data from this trial. Unless stated otherwise, the term “descriptive statistics” refers to number of subjects (N), number of observations (n), arithmetic mean, median, standard deviation (SD), first quartile (Q1), third quartile (Q3), minimum, and maximum for continuous data, and frequencies and percentages for categorical data. Certain figure presentations will include the standard error of the mean (SE). The term “treatment group” refers to treatment assignment in Trial CVL-865-SZ-001: Placebo, 7.5 mg BID CVL-865, 25 mg BID CVL-865 and assignment in Trial CVL-865-SZ-002: 25 mg BID CVL-865. All data collected from subjects who sign the informed consent form, including screen failures, will be included in data listings. Unless otherwise noted, the data listings will be sorted first by treatment, subject number and then by date within each subject number.

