5.7. Subject Disposition, Demographic and Baseline Characteristics

Subject disposition will be based on the Enrolled set population with tabulation of the number of subjects who complete the study, the number who discontinued from the study, reasons for discontinuation including the number of discontinues due to COVID-19 will be summarized. Additionally, the number of days on study for extension and double-blind will be summarized.

Number of subjects in each analysis population set will be summarized.

Demographic data and baseline characteristics including age, gender, childbearing potential, race, ethnicity and weight will be summarized using descriptive statistics for the Safety set.

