5.9. Medical History

Medical history events will be mapped to a Medical Dictionary for Regulatory Activities (MedDRA) version 27.1 or higher by preferred term and system organ class. Medical history will be summarized by treatment group using preferred terms and system organ classes. All events will be listed.

5.10. eDiary compliance

Exploratory efficacy variables are based on diary-collected seizure frequencies, and as such, diary compliance will be evaluated along with treatment compliance. Subjects are instructed to complete their diary entries at least once a day during the study. A diary day will be considered missing for compliance if a seizure diary record is missing for that day. Diary compliance will be evaluated during the Maintenance Phase and overall treatment period.

Diary compliance will be calculated as 100 times the number of diary days (i.e., days with completed diary assessments) during the period and dividing this quantity by the expected number of diary days that should have been completed during this period of time. Compliance is only computed for actual time of participation in the study up to the end of the Treatment Period. Only data prior to and on the date of last dose of study medication will be included in the compliance calculation. If a subject did not enter an analysis period, the diary compliance for the analysis period will not be calculated.

Diary compliance data will be listed and sorted by treatment group and subject.

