5.11.2. Exploratory Efficacy Analysis Approach

All Exploratory Efficacy Analysis endpoints will be summarized on the Efficacy Set.

Descriptive statistics will be provided for each efficacy endpoint and will be summarized at each trial visit using available data. Focal onset seizure frequency per week and 8 week period over the maintenance phase will include change from baseline. Baseline is derived from Trial CVL-865-SZ-001 and will be adjusted to an appropriate frequency for comparison. Any period which does not maintain greater than 20% diary compliance will not be summarized. Seizure rate over time will be displayed as adjusted frequencies over the maintenance phase. CGI-S will be displayed separately as change from baseline and change from Double-Blind Baseline. Baseline (Extension) is defined as the last assessment prior to the initiation of IMP in CVL-865-SZ-002. Double-Blind Baseline will be the baseline value from study CVL-865-SZ-001.

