9.3. Programming Conventions

- Page orientation, margins, and fonts: Summary tables, listings, and figures will appear in landscape orientation. There should be a 1.0" boundary on the left and right edges. The top and bottom margins are 1.0" for tables and listings but may vary for figures. Output should be printed in Courier New with a point size of 8.
- Identification of analysis population: Every summary table and figure will clearly specify the analysis population being summarized. Listings will be prepared for all subjects randomized.
- Group headers: In the summary tables, the group headers will identify the within-group sample size for the indicated analysis population. Of note, the header's sample size does not necessarily equal the number of subjects actually summarized within any given summary module; some subjects in the analysis population may have missing values and thus may not be summarized.
- Suppression of percentages corresponding to null categories: When count data are presented as category frequencies and corresponding percentages, the percent should be suppressed when the count is zero in order to draw attention to the non-zero counts.
- Presentation of sample sizes: Summary modules should indicate, in one way or another, the number of subjects actually contributing to the summary statistics presented in any given summary module. As mentioned above, this may be less than the number of subjects in the analysis population.
 - In the quantitative modules describing continuous variables (and thus presenting sample size, means, and standard deviations), the sample size should be the number of non-missing observations
 - For categorical variables that are presented in frequency tables, the module should present the total count in addition to the count in each category. Percentages should be calculated using this total as the denominator, and the percentage corresponding to the sum itself (that is, 100%) should be presented so as to indicate clearly to a reviewer the method of calculation.
- Sorting: Listings will be sorted by subject number and date, if applicable. If a listing is sorted in a different manner, it will be indicated on the listing shells.

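### Seizure freedom has no follow-up requirement, so on the natural reading an early dropout with no recorded seizure counts the same as a 52-week completer (low, optional)

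*SAP*

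**What the plan says.** SAP 3.1.2 contains the whole definition: "Seizure freedom will be represented as a binary outcome defined as having no seizures during the maintenance period". It states no completion condition, no minimum time and no rule for subjects who leave.

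SAP 4.2 fixes what the maintenance period is: "The start and end dates of each analysis period (following the study design) are used for the classification of efficacy data". Table 3 starts the phase at Day 15 and ends it at the earliest of the day before Visit 15 (Day 379), the day before early termination, or end of treatment. Its footnote, for subjects who terminate early and go on to taper, repeats that "end dates will be bound by early termination minus 1".

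The only data threshold for efficacy summaries is in SAP 5.11.2: "Any period which does not maintain greater than 20% diary compliance will not be summarized". SAP 5.10 sets the denominator for that figure: "Compliance is only computed for actual time of participation in the study up to the end of the Treatment Period".

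SAP 5.11.2 summarizes all exploratory efficacy endpoints on the Efficacy Set using available data. SAP Table 8 admits to that set anyone dosed who has one post-baseline seizure diary entry. Protocol Table 1 and section 9.4.2 add no rule for dropouts.

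**The concern.** Seizure freedom is listed under the long-term efficacy objective. The chance of recording no seizure falls steeply as follow-up lengthens, so a binary outcome without a fixed observation time mixes very different achievements. SAP 3.1.1, directly above, divides seizure counts by days with non-missing counts. The endpoint that depends most on follow-up gets no such adjustment.

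If early leavers are scored on their shortened period, leaving early can itself produce a success. The reported percentage would then overstate how many subjects stayed seizure-free for a year, and the percentage alone would not show it.

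**Working it through.** **Length of the period.** Day 15 to Day 378 is 378 − 15 + 1 = 364 days, or 52.0 weeks, which agrees with the ~52 weeks in Table 3.

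**One dropout traced through the rules.** A subject who terminates at Day 22 has a maintenance period of Days 15 to 21, which is 7 days. The diary rule needs more than 0.2 × 7 = 1.4 days, so 2 diary days are enough, and a complete diary scores 100%. With no recorded seizure this subject meets SAP 3.1.2. At an assumed 2 seizures per 28 days, the chance of no seizure is exp(−2 × 7/28) = 0.61 over 7 days, against exp(−2 × 364/28) = 5.1 × 10⁻¹² over 364 days.

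**Model for the size.** The documents give no seizure or dropout rates, so these inputs are assumptions:
- Daily seizure rate r = (m/28) × exp(sZ), with Z standard normal, median m = 2, 4 or 8 per 28 days, and log-SD s = 0.5 or 1.
- Dropout fraction d = 20%, 40% or 60%, uniform over T = 364 days and unrelated to seizures.
- Complete diaries.
- 120 subjects, the number SAP 1.2 expects to be eligible. Counts shrink if fewer enter maintenance.

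Completers scored seizure-free = (1 − d) × E[exp(−rT)]. Dropouts scored seizure-free = d × E[(1 − exp(−rT))/(rT)].

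**No drug effect (18 combinations).**
- Smallest (m = 8, s = 0.5, d = 20%): 0.218%, or 0.3 of 120.
- Middle (4, 1, 40%): completers 0.026% + dropouts 1.261% = 1.287%, or 1.5 of 120.
- Largest (2, 1, 60%): 3.826%, or 4.6 of 120.
- Dropouts make up 84% to nearly 100% of those scored seizure-free.
- If half of the dropouts leave after a recorded seizure, the range falls to 0.1% to 2.0% (0.1 to 2.4 of 120).

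**5% of subjects truly seizure-free.** Current reading = 0.05 + 0.95 × (no-effect total). Dropouts counted as failures = 0.05 × (1 − d) + 0.95 × (no-effect completers). Truth = 0.05 + 0.95 × E[exp(−rT)]. The Kaplan-Meier column is the estimate at 364 days from 400,000 simulated subjects per row.

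| m, s, d | Truth | Current reading | Dropouts as failures | Kaplan-Meier |
|---|---|---|---|---|
| 8, 1, 20% | 5.00% | 5.30% | 4.00% | 4.95% |
| 4, 1, 40% | 5.04% | 6.22% | 3.02% | 4.98% |
| 2, 1, 60% | 5.28% | 8.63% | 2.11% | 5.24% |

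Dropouts are 25%, 51% and 76% of those counted under the current reading, but not all are miscounted. In the middle row, 0.05 × 40% = 2.0 points are truly seizure-free subjects who left, and 0.95 × 1.261% = 1.2 points are not.

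Over all 18 combinations with 5% true responders, the current reading is closer to the truth than dropouts-as-failures in 15.

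**The case against.** The SAP never states how a dropout is scored. SAP 9.3 allows that "some subjects in the analysis population may have missing values and thus may not be summarized", so a programmer could treat a dropout's outcome as missing. A reader might infer that the plan deliberately credits dropouts with success, and the text does not go that far. But Table 3 governs efficacy data generally, and no passage says that a shortened period makes the outcome missing. Applying the written rules in order gives the shortened-period score. The ambiguity is a further reason to settle the wording.

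Other outputs reveal attrition. SAP 5.7 tabulates completers and days on study, and says that "reasons for discontinuation including the number of discontinues due to COVID-19 will be summarized". SAP 5.8 gives days on IMP and premature discontinuation. Seizure frequency is reported per 8-week period. SAP 5.1 adds that "All data collected from subjects who sign the informed consent form, including screen failures, will be included in data listings". This stands as mitigation, but no planned summary cross-classifies seizure freedom by length of follow-up.

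The strongest objection concerns the remedy. A reader might infer that the answer is to require completion and count every dropout as a failure. The working does not support that as the main definition: with 5% true responders it usually misses by more than the current reading does, in the opposite direction. It is clearly closer only when nobody is truly seizure-free. This objection is accepted.

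Finally, the endpoint is exploratory, SAP 5.3 states no hypothesis, and the primary objective is safety. That limits the weight of the point.

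**Conclusion.** The point holds as a low, optional improvement. Following SAP 3.1.2 with Table 3 gives a short-stay dropout with no recorded seizure the same score as a 52-week completer, and the diary rule does not prevent it. The percentage is biased upward as a measure of long-term seizure freedom.

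With no true seizure freedom, the expected number scored seizure-free is 0.3 to 4.6 of 120. With 5% truly seizure-free, the three tabulated scenarios overstate the proportion by about 0.3, 1.2 and 3.4 points. All of this rests on assumed seizure rates, assumed dropout unrelated to seizures, and complete diaries.

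A reader might infer that most subjects reported as seizure-free will be spurious, or that the trial's efficacy conclusions fail. The documents support neither. They give no rates from which to predict the mix, and no test or decision depends on this figure.

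**What to change.** In SAP 3.1.2 and 5.11.2:

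1. Make the main summary a Kaplan-Meier estimate of the proportion seizure-free at 52 weeks, using time to first seizure from Day 15, censored at the end of maintenance observation. State which seizures count and how the ±3-day visit window is handled, and show the number at risk.
2. Restrict it to Efficacy Set subjects who enter maintenance, and say so. SAP Table 8 also admits subjects who leave during titration, so this narrows the set named in SAP 5.11.2.
3. Beside it, give the binary count split into subjects who completed maintenance and subjects who stopped early, with observed duration. Take completion from the disposition record, because the schedule uses one label, Visit 15/ET, for both.
4. A percentage that counts dropouts as not seizure-free may be added, labelled as a conservative lower bound.

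The cost is SAP wording, one extra derivation and one extra summary from data already collected, settled before database lock. The Kaplan-Meier estimate assumes that dropout is unrelated to seizure risk. If subjects leave because seizures are coming back, it will be too favourable, and the split count helps a reader judge that. None of this repairs gaps within a diary: under the 20% rule a completer needs only 73 of 364 days (0.2 × 364 = 72.8), so diary completeness should be shown for those counted seizure-free.
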